Sildenafil in Heart Failure with Reactive Pulmonary Hypertension (Sildenafil HF)

PI: [name], PhD
CoInvestigators: [name]; [name]; [name], PhD
Statistician: [name]
Pharmacist: [name]
Sponsor: Gill Heart Institute

Scientific Rationale

In 2007, Lewis et al¹ from Massachusetts General Hospital published a paper on sildenafil, a type 5 phosphodiesterase inhibitor, in heart failure (HF). A single oral dose of 50 mg reduced resting and exercise pulmonary arterial pressure, systemic vascular resistance, and pulmonary vascular resistance, and increased resting and exercise cardiac index ($P < 0.05$ for all) without altering mean arterial pressure, heart rate, or pulmonary capillary wedge pressure. Peak VO_2 increased (15+/-9%) and ventilatory response to CO_2 output (VE/VCO₂ slope) decreased (16+/-5%) just one hour after sildenafil treatment. Improvements were confined to patients with secondary pulmonary hypertension (PH). The study group was 13 patients, which was enough to demonstrate statistical significance of the findings.

Pulmonary hypertension (PH) in heart failure (HF) is associated with poor outcomes. In a Mayo Clinic study, there was a strong positive graded association between pulmonary artery systolic pressure (PASP) and mortality. Increasing PASP was associated with an increased risk of death (hazard ratio [HR]: 1.45, 95% confidence interval [CI]: HR: 2.07, 95% CI: 1.62 to 2.64 for the highest PASP tertile versus lowest PASP tertile. This association was independent of age, sex, comorbidities, ejection fraction, and diastolic function².

Elevated right sided pressures in HF usually result from elevated left ventricular filling pressures. In HF, there are two major components of PH: hydrostatic and vasoreactive³. Hydrostatic, or the passive component, reflects the backward transmission of elevated left ventricular end diastolic pressure. Therefore, pulmonary artery diastolic pressure correlates tightly with the pulmonary capillary wedge pressure (PCWP). Normally, the pulmonary vasculature is characterized by low pressure, low resistance and high distensibility. It can accommodate a significant increase in blood flow with a minimal elevation of pulmonary arterial pressure. When this compensatory capacity is exceeded, there is an elevation in pulmonary arterial pressure. The effective treatment for such PH is diuretic therapy or other means of fluid removal.

The vasoreactive component of PH develops with long-standing PH. It is characterized by vasospasm, vasoconstriction, and eventually morphologic changes of the pulmonary vasculature. The degree of PH is considered "out of proportion" to the PCWP. In other words, PH persists independently of the PCWP. Pulmonary vascular resistance and the transpulmonary gradient are elevated. Diuretics are, therefore, ineffective for treatment of reactive PH, and other medical treatment options are limited. In HF, reactive PH is associated with worst outcomes. In one study involving HF patients, the presence of reactive PH carried a higher risk of death (HR: 1.55; 95% CL: 1.11, 2.20; $p < 0.001$)⁴.

Finally, no treatment option currently exists for reactive PH in the setting of HF. Multiple studies indicate that phosphodiesterase-5 inhibitors may be an effective therapy in this setting⁵⁻⁸. In particular, when patients with biventricular HF, poor right ventricular function, and increased transpulmonary gradient received sildenafil 20 mg three times a day, in addition to other HF medications, it resulted in a significant decrease of pulmonary pressures, improvement in right ventricular function, decrease in NTproBNP serum levels, as well a substantial improvement of the 6-minute walk distance by 91 ± 54 m.⁹ Importantly, there was a very modest reduction in pulmonary capillary wedge pressure, indicating that the reactive, and not the passive component of PH is the principal therapeutic target for sildenafil.

Clinical studies of sildenafil in HF are summarized in Table 1. The best results were obtained when the patients were selected based on the presence of reactive pulmonary hypertension, namely increased pulmonary vascular resistance and transpulmonary gradient.

No randomized controlled clinical trials, testing sildenafil in HF, selected patients based on these criteria. None of the trials, therefore, utilized the full potential of phosphodiesterase -5 inhibitors in HF. Specifically, the recent multicenter, double-blind, placebo-controlled, parallel-group, randomized RELAX trial included patients with unknown pulmonary pressures – they were not among inclusion criteria. Understandably, the trial failed to demonstrate favorable effects of sildenafil¹⁰.

Many physicians, treating patients with advanced HF, use sildenafil empirically, based on the literature. Phosphodiesterase-5 inhibitors for PH in HF is currently not approved by the FDA and is used as an off label indication in patients with HF. A randomized controlled trial including patients with appropriate criteria can demonstrate benefits of sildenafil in this common and growing condition.

Table 1. Clinical studies of sildenafil in heart failure, grouped by outcomes

Study/Date	Patients	N	PH	Intervention	Duration	Outcome
Positive						
Zakliczynski et al 2007 ¹¹ Case Series	Transplant candidates	6	TPG > 12 and/or PVR > 2.5 No reversibility with sodium nitroprusside	50 mg BID	1 month	3 - normal TPG and PVR 2 - acceptable responsiveness of pulmonary HTN to nitroprusside 1 – no difference
Guazzi et al, 2007 ¹²	NYHA II/III EF<45%	46	None	50 mg TID	6 months	Improved peak VO ₂ , endothelial function, symptoms
Dumitrescu et al, 2011 ⁹ Case series	Biventricular failure NYHA III/IV EF<40 TAPSE<17	9	PAP mean ≥ 25 PCWP ≥15 TPG >12	20 mg TID	5 months	Increased 6 minute walk distance, improved Echo, hemodynamics, BNP
Guazzi et al, 2011 ¹³ double-blind, randomized, placebo-controlled	HFpEF	44	PASP>40 by echo	50 mg TID	12 months	Improvement in QOL, symptoms, hemodynamics, echo
Pons et al, 2012 ¹⁴ retrospective	Transplant candidates	15	MPAP>25 PVR >2.5 and/or TPG >12	20-60 TID	5-6 months	MPAP, PVR, and TPG decreased. All successfully transplanted
Reichenbach et al, 2012 ¹⁵ non-randomized, retrospective case–control study	Transplant candidates	32	TPG>15	20-60 TID	~1 year	Improved hemodynamics, clinical status, 60% transplanted
De Santo et al, 2012 ¹⁶ prospective, non-randomized, open label uncontrolled pilot trial	Transplant candidates	31	PVR >6 WU, unresponsive to vasodilators	25 mg TID→ uptitrated every 2 weeks to 75 mg TID	3 months	All successfully transplanted

Guazzi et al, 2011 ¹⁷ Prospective, Randomized, Placebo- Controlled Study	NYHA II/III EF<40% E/e'>10	45	None	50 TID	12 months	Improved LV diastolic function and cardiac geometry, functional capacity and clinical status
Guazzi et al, 2012 ¹⁸ randomized, placebo-controlled	HF patients with exercise oscillatory breathing	32	None	50 TID	12 months	Improved peak VO ₂ , hemodynamics
Behling et al, 2008 ¹⁹ double-blind, randomized, placebo- controlled	Outpatients with HF, EF<40%	19	None	50 TID	4 weeks	Improved peak VO ₂ , decreased PASP
Negative						
Redfield et al, 2013 ¹⁰ double-blind, randomized, placebo- controlled	HFpEF	216 (113 sildenafil)	None	20 mg TIDx 12 weeks, followed by 60 mg TID for 12 weeks.	6 months	No improvement in exercise capacity or clinical status
Amin et al, 2013 ²⁰ double-blind, randomized, placebo- controlled	NYHA II/III EF<35%	106	None	25-50 mg TID	12 weeks	No improvement in exercise capacity or clinical status

1. Specific hypotheses

Phosphodiesterase- 5 inhibitors in heart failure with secondary reactive pulmonary hypertension improve exercise capacity, hemodynamic, echocardiographic parameters, and quality of life

2. Trial design

Patients over 18 years of age with HF who have PH by right heart catheterization (mean pulmonary artery pressure \geq 25 mm Hg, pulmonary capillary wedge pressure \geq 15 mm Hg, and pulmonary vascular resistance $>$ 3WU) will be eligible for randomization to sildenafil 20 mg, or placebo three times a day for 3 months. At baseline, a 6 minute walk test and quality of life questionnaire will be performed (Kansas City Cardiomyopathy Questionnaire) from 7 days prior to 3 days after qualifying right heart catheterization. If the echo was done for clinical indications within one month of enrollment, the data will be used. Laboratory tests are routinely obtained before right heart catheterization (comprehensive metabolic panel and NT-proBNP) and will be recorded for the study.

Participants will return for follow-up visits as needed for clinical indications. Our study coordinator will document changes of symptoms, changes in therapies, and capture clinical events like unscheduled hospital visits. For study purpose, the only follow-up visit will take place in 3 months. At that time, an echocardiogram, right heart catheterization, six minute walk, laboratory tests, and quality of life questionnaire will be repeated if clinically indicated. In addition, we will evaluate for signs and symptoms of HF (dyspnea, increased cough, paroxysmal nocturnal dyspnea, peripheral edema, S3 gallop, increased heart rate) at baseline and at the follow-up visit. These assessments are part of routine care for HF patients. The 3 month assessments should take place from 80-97 days following randomization whenever possible.

Measurements and calculations by 2D echo will include left ventricular end systolic and end-diastolic dimensions, left ventricular ejection fraction by Simpson's method, left atrial volume, severity of mitral and tricuspid regurgitation, velocity of tricuspid regurgitation, diameter of inferior vena cava and its variability with respirations, and right ventricular function by tricuspid annular plane systolic excursion.

Measurements by right heart catheterization will include right atrial pressure, right ventricular systolic and end diastolic pressure, pulmonary arterial systolic, diastolic, and mean pressure, and pulmonary capillary wedge pressure. Cardiac output and cardiac index will be calculated both by Fick and thermodilution methods.

The majority of study information will be collected from routine care for standard clinical indications.

Primary outcome

6 minute walk distance

Secondary outcomes

Percent of change of pulmonary arterial pressures (systolic, diastolic, and mean) and pulmonary vascular resistance from the baseline

Percent of change of cardiac index from the baseline

Percent of change in tricuspid annular plane systolic excursion

3. Objectives

Primary Objective:

The primary objective of this study is to determine whether sildenafil for treatment of HF with reactive PH can improve exercise tolerance measured by 6 minute walk distance

Secondary Objectives:

The secondary objectives of this study are to determine whether sildenafil for treatment of HF with reactive PH can improve hemodynamics, right ventricular function, or quality of life

4. Eligibility (include rationales for selecting or excluding particular cohorts)

Inclusion criteria:

[figure not shown]
- ≥ 18 years of age
- Known chronic heart failure appropriately treated with angiotensin converting enzyme antagonists, angiotensin receptor blockers, and beta blockers, unless contraindicated, not indicated, or poorly tolerated
- Indications for right heart catheterization, other than for biopsy
- Pulmonary artery mean pressure >25 mm Hg, pulmonary capillary wedge pressure >15 mmHg, and pulmonary vascular resistance >3 WU as measured by right heart catheterization within 3 days of planned randomization

Exclusion criteria:

- Hypersensitivity, allergy, or intolerable side effects of sildenafil
- Contraindication to sildenafil including need for nitric oxide donors such as organic nitrates or organic nitrates in any other form regularly and/or intermittently or current nitrate therapy
- History of primary PH, connective tissue disorders, severe COPD, pulmonary embolism, or left to right shunts
 - Primary (idiopathic) Pulmonary Hypertension in patients without history of heart failure
 - Pulmonary hypertension in patients with systemic scleroderma
 - Pulmonary hypertension due to congenital heart disease
 - Pulmonary hypertension due to severe COPD
 - Pulmonary hypertension in patients with systemic scleroderma
 - Pulmonary hypertension due to congenital heart disease
 - Pulmonary hypertension due to severe COPD or interstitial lung disease
- History of heart transplant, VAD, or any other solid organ transplant
- Likely to have solid organ transplant or any other major surgery during study enrollment/treatment period
- Liver cirrhosis as primary diagnosis

- History of massive pulmonary embolism
- Acute pulmonary embolism
- Female subject who is pregnant, breastfeeding, or one who is unwilling to practice an acceptable method of birth control unless postmenopausal or sterile.
- Unreliability as a study participant based on the investigator's (or designee's) knowledge of the subject (eg, alcohol or other substance abuse, inability, unwillingness to adhere to the protocol, documented non-compliance or vulnerable population
- Currently enrolled in another investigational drug or device clinical study, or less than 30 days since completing study
- Current diagnosis of HIV or AIDS
- End stage renal disease undergoing dialysis
- End stage liver disease
- Co-morbidities, if it limits exercise tolerance
 - morbid obesity (BMI>40)
 - COPD with oxygen dependence
 - severe peripheral vascular disease with intermittent claudication
 - status post amputation of lower extremity(s) at any level
 - severe degenerative joint disease preventing normal walking
 - CVA with long term sequella affecting ability to walk

5. Arms/regimens

6. Statistical design in detail (include one primary and any secondary endpoint(s), any stratification to be used in the randomization, sample size with power justification, analysis plan including plans for formal interim analysis, projected monthly accrual rate)

Sample size was calculated at 32 patients per arm, 64 patients total

Primary and secondary endpoints are as noted above. Patients will be randomized to treatment versus placebo in a 1:1 ratio using permuted blocks of variable size, to which the principal investigator (and the patients themselves) will be blinded. Planned sample size is 64, as described below. Data will be analyzed on an intent-to-treat basis, as described below. An interim analysis will also take place after data have been acquired for (approximately) 32 subjects, using a temporary alpha of 0.01 to mitigate inflation of Type I error probability due to multiple testing. Results of interim data analysis will be shared with Data Safety Monitoring Board, which will advise the principal investigator on whether to continue with the study.

Planned sample size of 64 will provide nearly 80% power, using the final alpha of 0.05, to detect a difference between groups on a numerical outcome variable for which the effect size is approximately 0.7, in the sense that a typical person in the treatment group would be approximately seven-tenths of one standard deviation better than a typical person in the control group. This is slightly greater than the effect size of approximately 0.6 observed by Mathai and colleagues for the exercise endpoint, but we anticipate being able to reduce variability by considering change scores from baseline to 3 months rather than just the final results at 3 months.

Each numerical outcome variable will be examined for approximate normality, and appropriate corrective action (e.g., log transformation prior to further data analysis) will be considered if approximate normality is untenable. A linear mixed model will be fit relating each outcome variable to group (between-subjects factor: treatment vs. placebo) and time (within-subjects factor: baseline vs. 3 months), with random effects for subjects and embedded linear contrasts to compare groups on change from baseline to 3 months. Although randomization is anticipated to balance groups on demographic and clinical characteristics, in the unlikely event that groups are imbalanced we can modify the linear mixed modeling to adjust for any covariates on which groups are imbalanced. Loss to follow-up is anticipated to be small, but in the unlikely event of more than 10% attrition from either group we can employ multiple imputation or another method for handling missing data. Groups will be compared on adverse events (e.g., re-hospitalization) using Fisher's exact test.

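### Patients already taking a phosphodiesterase-5 inhibitor are not excluded, so current users can be randomized and, if they continue the drug, pull the treatment comparison toward no effect

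*Combined protocol and SAP*

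**What the plan says.** The Scientific Rationale describes existing practice: "Many physicians, treating patients with advanced HF, use sildenafil empirically, based on the literature". It adds that the drug class, though not approved for pulmonary hypertension in heart failure, "is used as an off label indication in patients with HF".

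Section 4 (Eligibility) names sildenafil in two exclusions. One is "Hypersensitivity, allergy, or intolerable side effects of sildenafil". The other begins "Contraindication to sildenafil including need for nitric oxide donors such as organic nitrates" and goes on to nitrates in other forms. Two further criteria come close to the subject without reaching it:

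- The other-study exclusion reads "Currently enrolled in another investigational drug or device clinical study, or less than 30 days since completing study". It covers trial participation, not a clinician's off-label prescription.
- The background-therapy inclusion criterion reads "Known chronic heart failure appropriately treated with angiotensin converting enzyme antagonists, angiotensin receptor blockers, and beta blockers", with allowance for patients in whom these are unsuitable. It does not mention phosphodiesterase-5 inhibitors.

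For the period after randomization, Section 2 (Trial design) says "Our study coordinator will document changes of symptoms, changes in therapies". It sets no rule on open-label use of the class. Section 6 specifies an intent-to-treat analysis comparing the arms on change from baseline to 3 months. It names no stratification factor and no planned adjustment for use of this class.

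**The concern.** The primary objective is to learn whether sildenafil improves walk distance. That requires the two arms to differ in exposure to the drug. A current user assigned to placebo who continues the prescription is on active treatment. A current user assigned to sildenafil adds study drug to existing treatment of the same class, and the baseline walk already contains whatever benefit that treatment gave. In both cases the change from baseline carries less of the effect the trial is designed to measure.

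Intent-to-treat analysis correctly keeps these patients in. The adjustment for imbalanced covariates offered in Section 6 does not help, because the difficulty is missing contrast within both arms and not an imbalance between them. What is at stake is a diluted estimate, and a higher chance of a null result, in a trial whose sample size has no reserve.

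**Working it through.** **Inputs from Section 6.** 32 patients per arm, 1:1 allocation, final alpha 0.05, effect size 0.7 SD, power stated as nearly 80%. Sidedness is not stated.

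**Step 1: reproduce the stated power.** For a two-sided two-sample t-test with n = 32 per arm:

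- degrees of freedom = 2 × 32 − 2 = 62, critical value 1.999
- noncentrality = 0.7 × √(32/2) = 0.7 × 4 = 2.80
- power = 78.7% (79.96% by the normal approximation)

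Both agree with the plan. A one-sided test would give 87.0%, which does not, so two-sided 0.05 is taken as the plan's intention. By the t calculation, 80% power needs 34 per arm, so there is no margin at 32.

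**Step 2: check whether a current user is eligible.** Take a patient with chronic heart failure who has been prescribed sildenafil off label, tolerates it, takes no nitrates, is in no other study and meets the catheterization thresholds. The intolerance exclusion does not apply. The contraindication exclusion does not apply on its stated content. The other-study exclusion does not apply. The background-therapy criterion is silent. Nothing else in Section 4 refers to the class, and no washout is described.

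**Step 3: dilution model.** Let f be the share of randomized patients already on the class, equal in both arms, and k the fraction of the 0.7 SD effect that they still show. With the SD held at 1:

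average effect = 0.7 × [1 − f(1 − k)]; noncentrality = 4 × average effect

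Neither f nor k is given in the documents. Both are assumptions here. With k = 0:

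| f | average effect (SD) | noncentrality | power, 32 per arm | n per arm for 80% |
|---|---|---|---|---|
| 0% | 0.70 | 2.80 | 78.7% | 34 |
| 5% | 0.665 | 2.66 | 74.5% | 37 |
| 10% | 0.63 | 2.52 | 69.9% | 41 |
| 20% | 0.56 | 2.24 | 59.7% | 52 |
| 30% | 0.49 | 1.96 | 48.8% | 67 |

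**Step 4: relax the zero-contrast assumption.** With k = 0.5, f(1 − k) is halved. At f = 10% the average effect is 0.7 × 0.95 = 0.665 SD and power is 74.5%. At f = 20% it is 0.7 × 0.90 = 0.63 SD and power is 69.9%. At f = 30% it is 0.7 × 0.85 = 0.595 SD and power is 64.9%.

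**The case against.** The strongest reply is that the size of the problem is assumed throughout. That stands, in several parts.

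- **Frequency.** A reader might infer that a large part of the recruited population will already be on the drug. The protocol makes a statement about physicians who treat advanced disease. It gives no share of patients, and none for this trial's screening pool. Shares below 5%, including zero, are compatible with the text.
- **Zero contrast.** This is the unfavorable end. It presumes that users continue open-label drug, which the documents do not say. A user who stopped at entry, or who gained from added study drug, would contribute some contrast.
- **Hemodynamic thresholds.** Patients must still show raised mean pulmonary pressure, wedge pressure and vascular resistance at catheterization. On the protocol's own premise that sildenafil lowers pulmonary pressures, some users who responded well would fail these limits. That makes high shares less likely, but it does not bar users whose pressures remain raised on treatment.
- **Open-ended wording.** The contraindication exclusion is introduced with the word including, so an investigator could read existing treatment with the same class into it. The text does not say so, and an unwritten screening rule cannot be applied consistently or audited.
- **Direction.** Under this model users pull the estimate toward zero. They do not inflate the type I error or create a false benefit.
- **Missing content.** A figure is absent at the head of the eligibility section, and Section 5 shows no text in the copy reviewed. A statement on concomitant treatment there cannot be wholly ruled out. The exclusion list itself shows no such gap.

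A reader might also infer a safety finding from the possibility of duplicate exposure. The documents give no figure on harm from it, so none is claimed here.

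These points limit the size. They do not close the gap: as written, the criteria admit current users.

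**Conclusion.** The concern holds as an omission in eligibility with a predictable direction and an unknown size. The protocol describes empirical off-label use of the study drug, does not exclude patients already receiving the class, and would keep them in the primary comparison. If they continue open-label treatment, the estimate is biased toward no effect relative to what the drug would do in untreated patients.

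The power figures illustrate sensitivity and are not a forecast. They rest on an assumed user share, equal shares in both arms, no contrast in users and an unchanged SD. A reader might take the 48.8% figure to mean that the trial is expected to have about even odds of success. The documents do not support that, since the 30% share behind it is arbitrary. What they do support is that the plan starts at 78.7% by the t calculation, so even a 5% share of zero-contrast users takes about 4 points (78.7 − 74.5 = 4.2).

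This should be corrected before enrollment, because an eligibility gap cannot be repaired once such patients have been randomized.

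**What to change.** Add one line to the exclusion criteria in Section 4: current treatment with any phosphodiesterase-5 inhibitor at screening. Whether a look-back period is needed, and how long it should be, is for the investigators to decide.

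The eligibility line cannot prevent open-label starts after randomization. Tabulate these by arm from the therapy changes that the coordinator already records, so that readers can judge how far the contrast was eroded. Keep every randomized patient in the intent-to-treat analysis.

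The cost is one sentence, one table and a slightly smaller screening pool. If recruitment still reaches 32 per arm, the planned 78.7% at 0.7 SD is unchanged. If excluded users could not be replaced, so that 32 × (1 − f) per arm remained at the full 0.7 SD, power would be 74.2% at f = 10% and 69.0% at f = 20%. That is better than retaining zero-contrast users (69.9% and 59.7%), and about the same as retaining users who keep half the effect (74.5% and 69.9%).

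### The 3-month six-minute walk, the only primary outcome, is required only when clinically indicated, so neither the intent-to-treat comparison nor the 64-patient power is secured

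*Combined protocol and SAP*

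**What the plan says.** Section 2 (Trial design) treats the two time points differently. For baseline it is unconditional: "At baseline, a 6 minute walk test and quality of life questionnaire will be performed". For 3 months, which it describes as the only follow-up visit held for study purposes, it lists the echocardiogram and then: "right heart catheterization, six minute walk, laboratory tests, and quality of life questionnaire will be repeated if clinically indicated". On timing it adds: "The 3 month assessments should take place from 80-97 days following randomization whenever possible".

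Section 2 gives walk distance as the sole primary outcome. The primary objective in section 3 is whether sildenafil "can improve exercise tolerance measured by 6 minute walk distance". Quality of life is a secondary objective there.

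Section 6 (Statistical design) states: "Data will be analyzed on an intent-to-treat basis, as described below". The contrast is the difference between arms in change from baseline to 3 months, from a linear mixed model. On size: "Planned sample size of 64 will provide nearly 80% power, using the final alpha of 0.05", for an effect of about 0.7 SD. The step up from about 0.6, seen in an earlier study, is justified by "considering change scores from baseline to 3 months rather than just the final results at 3 months". Loss to follow-up is expected to be small, and "in the unlikely event of more than 10% attrition from either group we can employ multiple imputation or another method for handling missing data".

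**The concern.** A change score needs both a baseline and a 3-month walk. Read literally, section 2 lets staff omit the second one, without a protocol deviation, in any patient for whom no clinical reason is recorded. Since this is the only study follow-up visit, no later measurement can fill the gap.

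Two things are at stake. The first is numbers: the sample size assumes that all 64 patients contribute, and nothing was added for missing walks. The second is selection: whether a test is indicated is decided after randomization and reflects how the patient is doing, so the tested patients need not represent those randomized. The missing-data clause in section 6 is framed as attrition, which does not clearly cover a patient who attends and is not tested. It names no definite method, and both the mixed model and standard multiple imputation rely on data being missing at random. That is doubtful when testing follows clinical state.

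**Working it through.** **Does any text require the 3-month walk?** Three statements come close. The visit is held for study purposes, but that fixes the visit, not its content. The 80-97 day window sets timing and applies only where possible. Section 2 also says the assessments belong to routine care, which describes practice and imposes no duty. None removes the condition.

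**Inputs from section 6.** 32 per arm, 1:1 allocation, effect size d = 0.7, final alpha 0.05. Sidedness is not stated; two-sided is assumed because it reproduces the plan's figure (one-sided gives 87-88%).

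**The plan's own figure.** The noncentrality is d × √(n/2) = 0.7 × √16 = 2.80.
- Normal approximation: Φ(2.80 − 1.96) = Φ(0.84) = 80.0% (79.96% unrounded).
- Noncentral t, 62 df, critical value 1.999: 78.7%.

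Both agree with the plan's claim. On the t calculation 33 per arm gives 79.97% and 34 gives 81.2%, so there is no reserve.

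**Scenario A: walks omitted at random, equally in both arms.** Same formula, with n replaced by the number tested per arm.

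| Share tested (assumed) | Tested per arm | Noncentrality | Power |
|---|---|---|---|
| 100% | 32 | 2.80 | 78.7% |
| 90% | 28.8 | 2.66 | 74.2% |
| 75% | 24 | 2.42 | 66.1% |
| 50% | 16 | 1.98 | 48.3% |

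**Scenario B: testing depends on the walk change.** Change is taken as N(0, 1) on placebo and N(0.7, 1) on sildenafil. The probability of being tested is expit(a + s × change), with a chosen to give the overall share tested. Power uses the expected number tested in each arm and the pooled SD of the tested. For s = 1 or s = −1 (the sign makes no difference):

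| Share tested | Difference, original SD | Pooled SD of tested | Standardised effect | Power |
|---|---|---|---|---|
| 90% | 0.65 | 0.97 | 0.68 | 71% |
| 75% | 0.61 | 0.94 | 0.65 | 60% |
| 50% | 0.58 | 0.91 | 0.64 | 41% |

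With s = −1 the shares tested (placebo/sildenafil) are 92.8/87.2%, 80.5/69.5% and 57.2/42.8%; s = +1 mirrors them. Against Scenario A, selection costs about a further 3, 6 and 8 points of power. Most of the loss is lost numbers.

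**Range over slopes 0.5 to 2.** At 75% tested: 0.67 to 0.51 SD, power 64% to 52%. At 50% tested: 0.66 to 0.44 SD, power 46% to 32%.

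These figures use a t-test on patients with both walks in place of the planned mixed model. The gap should be small, because a patient with only a baseline value adds little to a change contrast.

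**The case against.** The strongest reply is loose drafting. One sentence covers five procedures, one of them an invasive catheterization, and the condition may have been written with that one in mind. A study visit with a window, and an analysis built on change scores, suggest that everyone was meant to walk. That may well be the intention, but the text does not say it, and the unconditional baseline wording shows how it could have been said. If it is the intention, the correction only records it.

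The second reply concerns bias. Patients and the principal investigator are blinded. If whoever judges indication is also blinded and sildenafil does nothing, both arms face the same selection and the expected difference stays at zero. The model above shows attenuation only, which means a missed effect and not a false positive. This stands and limits what can be claimed. The protocol does not, however, mention blinding of other staff.

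Third, the selection model is assumed and rather pessimistic. If indication depended on baseline status instead, the mixed model could use that information. This also stands: Scenario B is an illustration. The defect does not depend on it.

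Finally, the power argument belongs to the walk alone. The questionnaire is included because it serves a secondary objective and falls under the same condition.

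**Conclusion.** The concern holds and should be corrected before the trial relies on this plan. The sample-size arithmetic is sound; what is missing is a requirement to make the measurement it depends on. If all 64 patients walk at 3 months, power is as stated. If testing follows clinical indication, the primary comparison rests on a subset formed after randomization. Power then falls to between 74% and 48% from lost numbers alone when 90% to 50% are tested, and to between 71% and 41% with outcome-dependent testing at slope 1, where the estimated effect is also diluted. The retest shares and slopes are assumptions, as is two-sided testing; the documents give no basis for choosing among the scenarios. Confidence is high about the wording. The size of the consequence depends on practice at the site.

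**What to change.** In section 2, take the six-minute walk and the questionnaire out of the conditional list. Suggested text:

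> The walk test and the Kansas City Cardiomyopathy Questionnaire are study procedures. Both will be obtained from every randomized patient at the 3-month visit (days 80-97), irrespective of clinical indication and of whether study drug is still being taken.

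The clause on study drug is there because the analysis is by intent-to-treat. The cost is one protocol sentence, plus a non-invasive test and a questionnaire at a visit already scheduled. Recruiting more patients is a poorer remedy: keeping 32 tested per arm would need 32/0.75, or 43 per arm, at 75% tested and 64 per arm at 50%, and would leave the selection in place.

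The existing condition on the echocardiogram, catheterization and laboratory tests is left alone here. It does leave the listed secondary outcomes (pulmonary pressures and resistance, cardiac index, tricuspid annular excursion) exposed in the same way. The sponsor should reconcile those passages and report by arm how many patients had each test repeated.

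Useful but optional: a fixed missing-data method in place of the 10% trigger, and a prespecified sensitivity analysis for patients who died or could not walk.
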